3.1. Treatment Center Inclusion

Subjects will be enrolled in from Unity Point Health-Meriter Hospital Labor & Delivery. Patients will be approached for recruitment in the postpartum period.

3.2. Patient inclusion and exclusion

- **Aim 1:**
 - 3.2.1.1 Inclusion**
- Hypertensive disorders of pregnancy including gestational, chronic, or preeclampsia diagnosed in the antenatal (primary admission for delivery of the baby (planned or due to hypertension) or postpartum period as determined by SBP ≥ 140 or DBP ≥ 90 on two occasions ≥ 4 hours apart. (Refer to section 3.3 for diagnosis criteria).
- Gestational age at time of delivery ≥ 23 weeks gestation
- Primary hospital admission for the delivery of the neonate(s).
- Age ≥ 18 years.

3.2.1.2 Exclusion

- Inability to obtain informed consent

- **Aim2-5:**

3.2.1.3 Experimental

3.2.1.3.1 Inclusion

- Hypertensive disorders of pregnancy including gestational, chronic, or preeclampsia diagnosed in the antenatal (primary admission for delivery of the baby (planned or due to hypertension) or postpartum period as determined by SBP ≥ 140 or DBP ≥ 90 on two occasions ≥ 4 hours apart. (Refer to section 3.3 for diagnosis criteria).
- Gestational age at time of delivery ≥ 23 weeks gestation
- Primary hospital admission for the delivery of the neonate(s).
- Age ≥ 18 years.

3.2.1.3.2 Exclusion

- Inability to obtain informed consent

3.2.1.4 Control group:

3.2.1.4.1 Inclusion: we will have an opt out policy (see 4.4.1 below) to maximize all patients to be included to provide an adequate 1:1 comparison control group (see form).

3.2.1.4.2 The same inclusion criteria from 3.2.1.3 will be used to define the control group subjects included.

- Hypertensive disorders of pregnancy including gestational, chronic, or preeclampsia diagnosed in the antenatal (primary admission for delivery of the baby (planned or due to hypertension) or postpartum period as determined by SBP ≥ 140 or DBP ≥ 90 on two occasions ≥ 4 hours apart. (Refer to section 3.3 for diagnosis criteria).
- Gestational age at time of delivery ≥ 23 weeks gestation
- Primary hospital admission for the delivery of the neonate(s).
- Age ≥ 18 years.

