1.3 Motivation for this study

Hospital readmission was more common in patients with mild hypertension prior to their primary delivery discharge. In addition, Hirshberg, et al discovered postpartum patients were less likely to be readmitted due to hypertension related complications if they were discharged on antihypertensive medication therapy. Treatment or surveillance strategies have been understudied for postpartum patients with hypertension. Demonstration of a decrease in hospital readmission with a novel mobile application may provide an effective method of preventing severe maternal postpartum hypertension related hospital readmission and associated maternal morbidities.

2. Objectives

Aim 1: Conduct an initial phase study for postpartum women at risk for severe hypertension to estimate the rates of willingness to participate in and utilize remote mobile health applications to monitor home blood pressures and weights, medication adherence after hospital discharge, to inform a trial to decrease postpartum maternal morbidity and readmission.

Sub Aim 1: Conduct a survey regarding patient satisfaction using mobile health technology

Hypothesis: We hypothesize that the mobile health application will be implemented with strong fidelity, have positive patient acceptability, and demonstrate a meaningful reduction in home blood pressures and postpartum hospital readmission.

Aim 2: Obtain prospective daily monitoring of blood pressures in the Peripartum period (initial hospital admission through 6 weeks postpartum) to understand natural history of development and resolution of postpartum hypertension using all patients utilizing the mobile health program over year 1. Specifically, this data will be used to estimate standard deviations of SBP and DBP in the intrapartum compared to 24-96 hours postpartum to inform a future trial regarding the threshold blood pressure to prevent development of severe hypertension or hospital readmission.

Hypothesis: We hypothesize women with severe intrapartum hypertension will predict development of severe hypertension within 7 days of delivery more often than blood pressures obtained in the first 24-96 hours after delivery.

Aim 3: Compare the maternal outcomes in the cohort utilizing remote patient monitoring to the cohort of patients with hypertension related disorders discharged with routine care. This would include all patients from Aim 1 as well as the remaining from the entire 1-year experimental period.

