3.2.1.5 Exclusion

- Inability to obtain informed consent

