4.2. Screening for eligibility and consent

For aims 1-5

Inpatient

We will screen for subjects on a daily basis by reviewing the patients admitted to postpartum unit. Patients will be approached if the electronic medical record indicates a diagnosis of hypertension or the patient meets the blood pressure criteria for enrollment. This screening will be performed by the mobile health nurse providing support for this program or the research coordinator as needed. If a patient is identified, the patient's nurse or care provider will be contacted to ask the patient if they are interested in learning more about the study.

Outpatient

I have also met with the providers providing obstetrical care to patients (midwives and physicians who practice at UW Health- [name], UW Health- Fitchburg, UW Health- West, UW Health- West Towne, UW Health- Union Corners, Associated Physicians) who express interest in providing this experimental clinical program for their patients. Providers may discuss this project with their patients who have hypertension affecting their pregnancy. They will also have access to the patient brochure and can give this to the patients they believe meet criteria for the study. If they identify a patient who is interested in participating they will directly contact a member of the research team to further discuss enrollment with the patient. In addition, the floor nurses will know the inclusion criteria and may contact a member of the research team for recruitment, however this is not expected.

Finally, a patient can inquire and express interest in participating the program and contact the research coordinator directly with the phone number contact provided in the study flier. The patient inclusion and exclusion criteria will be verified as well as the participant's interest in the study. The informed consent process will be conducted by trained research staff and will include all aspects of the study and full disclosure of the risks, benefits, and alternatives. The study consent and HIPPA authorization form (see appendix) will be signed after all questions have been discussed and answered.

4.3. Data management:

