4.4. Recruitment and retention

- **Staff**

- 4.4.1. Staff training and education prior to initiation of the trial for active members of the study team.
- 4.4.2. General education regarding the trial to all staff providers (physicians, nurses, medical assistants to enhance support of the trial).
- 4.4.3. Staff education on a 6-month schedule for new staff and further training as needed.
- 4.4.4. Interval reports back to participating faculty/nurses to share stories of success or patient feedback to encourage continued participation.
- **Study subjects**
 - 4.4.1. We will place a study information sheet titled “The UnityPoint Health-Meriter Hypertensive Study” in the patient enrollment paperwork for all patients admitted to Labor and Delivery. This will sheet will allow research staff to collect data on all patients with respect to their hypertension diagnosis in the Peripartum period. We will be using this data primarily for the control group for aims 2-3.
 - 4.4.2. Once a patient is identified and agrees to participate we will give them a separate patient brochure to further detail the study. This will be directly given to the patients by their nurse once admitted to the postpartum unit.
 - 4.4.3. A member of the research team trained in consenting procedures will then meet with the subject to review the informed consent document. After the researcher reviews the document, the subject will be allowed to ask questions and given sufficient time to contemplate participation. If the patient chooses to participate, they will sign the informed consent document.
 - 4.4.4. Incentives: Subjects will be given a pack of diapers at enrollments and a \$15 gift card at completion of the study (6 weeks PP visit) to encourage completion of the trial endpoint.
 - 4.4.5. Care reminders will be sent via the Honeywell Genesis Device by the UnityPoint at Home telehealth nurse. The purpose of this is to remind and encourage daily vital reporting.
 - 4.4.6. Patient surveys for understanding how to improve the system

5. Pre-enrollment evaluation

- 5.1. Prior to enrollment, the mobile health nurse or research staff will confirm diagnoses utilizing the table above.
- 5.2. If the subject agrees to participate, the research coordinator will obtain informed consent.

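### Control criteria set no explicit requirement that hypertension be diagnosed before delivery discharge; if late-diagnosed women with a higher readmission risk were selected as controls, the readmission comparison would lean toward monitoring

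*Combined protocol and SAP*

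**What the plan says.** Section 3.2.1.4.2 carries the monitored arm's criteria over to the controls: "The same inclusion criteria from 3.2.1.3 will be used to define the control group subjects included". The hypertension bullet requires a disorder "diagnosed in the antenatal (primary admission for delivery of the baby (planned or due to hypertension) or postpartum period". Its first parenthesis is never closed, and the postpartum period is given no end. A separate bullet reads "Primary hospital admission for the delivery of the neonate(s". The only control exclusion, in section 3.2.1.5, is "Inability to obtain informed consent".

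Control data come through an information sheet handed out at Labor and Delivery admission. Section 4.4.1 (study subjects) says the sheet lets staff "collect data on all patients with respect to their hypertension diagnosis in the Peripartum period" and adds "We will be using this data primarily for the control group for aims 2-3". Aim 2 in section 2 uses the phrase "Peripartum period (initial hospital admission through 6 weeks postpartum". Section 7.1 matches controls 1:1 to monitored women within the same month and names no other matching factor.

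For monitored women, the inpatient route in section 4.2 is "We will screen for subjects on a daily basis by reviewing the patients admitted to postpartum unit", and section 6 starts home measurements at hospital discharge. Section 4.2 also has outpatient-provider and self-referral routes, which do not expressly rule out later enrollment.

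Appendix I, item 34, records when the disorder was diagnosed. Code 34c covers any diagnosis after delivery, with no discharge cutoff. Code 34d covers women diagnosed only at a readmission.

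**The concern.** One set of criteria is applied in two different ways. For monitored women it is mostly applied forward in time, during the delivery stay. For controls it is applied to charts, when everything up to six weeks postpartum may already be on record. A control who enters because hypertension was first found at, or just before, a readmission has been selected partly on the outcome. A monitored counterpart is unlikely, though not excluded.

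Readmission matters to several parts of the plan. It is in the hypotheses of Aims 3 and 5, it is one of the primary outcomes of the Aim 4 cost analysis (section 7.2), and section 14 names hypertension readmission within 42 days of delivery as the main outcome. Aims 2-5 are exploratory and unpowered, and their listed endpoint is enrollment. Even so, section 7.1 says the results will be used to plan further studies, so a spurious difference could carry forward.

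**Working it through.** **1. Figures in the plan.** Section 7.1 plans 220 monitored women and 220 controls: 220 + 220 = 440, as stated. It later reports 214 of each. No readmission rate, alpha or power is given for Aims 2-5, so there is no power figure to reproduce.

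**2. Does any passage set a diagnosis cutoff?**
- Hypertension bullet, 3.2.1.4.2: allows a postpartum diagnosis. Depending on where the parenthesis should close, this may or may not be confined to the delivery admission.
- Delivery-admission bullet, 3.2.1.4.2: requires a delivery admission but does not date the diagnosis.
- Exclusion, 3.2.1.5: consent only.
- Aims 3 and 5: describe controls as women with the disorder who went home under routine care. This suggests diagnosis by discharge but is not an eligibility rule.
- Aim 4, section 7.2: describes routine care as a nurse visit a few days after discharge. Again, no rule.
- Items 34c and 34d: leave room for a diagnosis after discharge but do not define who may be a control.

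No passage states a cutoff, and none admits late-diagnosed women in terms.

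**3. Size, if any such controls exist.** Let n = 214 controls. The documents give none of the following, so all are assumed: p, the hypertension-readmission risk in women diagnosed before discharge; k, the number of controls first diagnosed later; f, the share of those k readmitted for hypertension. Assume no programme effect and no late-diagnosed women in the monitored group.

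Control rate = [p(n − k) + f·k] / n. Relative risk (monitored/control) = p / control rate.

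For p = 4%, k = 1, f = 1: (0.04 × 213 + 1) / 214 = 9.52 / 214 = 4.45%, and 4.00 / 4.45 = 0.90.

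| k | f | Control rate (p = 4%) | RR |
|---|---|---|---|
| 0 | – | 4.00% | 1.00 |
| 1 | 0.25 | 4.10% | 0.98 |
| 1 | 0.5 | 4.21% | 0.95 |
| 1 | 1 | 4.45% | 0.90 |
| 5 | 0.25 | 4.49% | 0.89 |
| 5 | 0.5 | 5.07% | 0.79 |
| 5 | 1 | 6.24% | 0.64 |

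Varying p with k = 1 and f = 1: at p = 2%, 5.26 / 214 = 2.46%, RR 0.81; at p = 6%, 13.78 / 214 = 6.44%, RR 0.93. The far corner, p = 2%, k = 5, f = 1, gives 9.18 / 214 = 4.29% and RR 0.47, but it needs all three assumptions together.

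**4. Direction.** Each late-diagnosed control shifts the control rate by (f − p) / n. At f = 1 and p = 4% this is 0.96 / 214, or 0.45 percentage points. If f = p there is no shift: with p = 4%, 25 late-diagnosed controls of whom 1 is readmitted have f = 1/25 = 4%. If f < p the shift goes the other way. Bias toward monitoring therefore requires f > p.

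**The case against.** The strongest reply is that the protocol already means the delivery stay. Section 3.1 recruits from the hospital's Labor and Delivery unit, section 4.2 screens the postpartum unit, and section 6 starts identification at the delivery admission. In these places, postpartum mostly means before going home. The control criteria repeat the monitored-arm wording, including the delivery-admission bullet, so a reasonable reader could take them as judged at that admission. This stands as evidence of intent. It describes the monitored arm's procedures, however, and supplies no cutoff for controls found by chart review.

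A reader might infer from section 4.4.1 and Aim 2 together that the plan opens a six-week diagnosis window for controls. The documents do not support that. Aim 2's phrase sets the period of blood pressure monitoring, and section 4.4.1 describes an information sheet; neither is an eligibility rule. Likewise, a reader might take item 34d as showing that women diagnosed at readmission were eligible. It is an extraction field, possibly carried over from the earlier IRB request mentioned in section 3.4, and it also provides the means to exclude them.

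The later-entry routes in section 4.2 mean the asymmetry between groups may not be complete. The exploratory status of Aims 2-5 also limits what is at stake.

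**Conclusion.** The point holds in a conditional form. The criteria contain no explicit requirement that diagnosis precede delivery discharge, and the surrounding text leans both ways. Taken literally, they could admit controls selected partly on the readmission outcome. Bias toward monitoring needs two further conditions: that such controls were selected, and that they were readmitted for hypertension more often than other controls.

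A reader might go further and conclude that the comparison is biased, or that any late-diagnosed control who is readmitted must tilt it. Neither follows. The documents do not say whether any such woman is among the 214, and the net effect depends on f against p. The size is unknown. The figure of about 0.90 for one readmitted late-diagnosed control rests on an assumed 4% risk, no programme effect and none of these women in the monitored group; with k = 0 the figure is 1.00. The point is worth fixing because the check is cheap and can settle it. Confidence is medium because the wording is ambiguous.

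**What to change.** State in section 3.2.1.4.2, and for the monitored arm in 3.2.1.3.1, that the qualifying blood pressures or diagnosis must be recorded before discharge from the delivery admission. Close the parenthesis in the hypertension bullet to match.

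Accrual is closed, so apply the rule as a date check to the 214 controls and the monitored women. Exclude women coded 34d. For those coded 34c, compare the date of the qualifying readings or diagnosis with the primary discharge date and time (item 44), using the dated readings in items 58-69 where they suffice and the chart where they do not. Report the number excluded in each group and the readmission comparison with and without them. Keep the stated outcome window through 42 days postpartum.

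The cost is a clarifying sentence, a date comparison on fields already listed and a few chart checks. The downside is that a few matched pairs may be lost or need re-matching. If no such women are found in 34c or 34d, the point is closed.

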3.2.1.5 Exclusion

- Inability to obtain informed consent

3.3. Classification/diagnosis of hypertension related disorders in pregnancy

CHRONIC HYPERTENSION	
 • SBP ≥ 140 mmHg or DBP ≥ 90 mm Hg • Pre-pregnancy or before 20 weeks
-----------------------------	--

GESTATIONAL HYPERTENSION	
 • SBP \geq140 mm Hg or DBP \geq90 mm Hg • Occurs after 20 weeks • Absence of proteinuria or systemic signs/symptoms consistent with preeclampsia
PRE-ECLAMPSIA	
 • New onset BP after 20 weeks • Two BPs SBP\geq140 or DBP \geq90 on two occasions at least 4 hours apart • AND Proteinuria with or without signs/symptoms* • OR in the absence of proteinuria new onset of any systemic finding: 
 -Thrombocytopenia (platelets <100,000K) -Renal insufficiency (serum creatinine $>$1.1 mg/dL) -Impaired liver function (\uparrowLFT 2x normal)
Eclampsia	
 • New onset grand mal seizures in woman with preeclampsia • New onset seizures 48-72 hours postpartum
Chronic Hypertension + SUPERIMPOSED PREECLAMPSIA	
 • Chronic hypertension in association with preeclampsia
PREECLAMPSIA WITH SEVERE FEATURES (one or more of the listed criteria)	
 • SBP \geq160 mm Hg or \geq110 mm Hg on at least 2 occasions at least 4 hours apart 
 -Thrombocytopenia (platelets <100,000K) -Renal insufficiency (serum creatinine $>$1.1 mg/dL) -Impaired liver function (\uparrowLFT 2x normal) 
 - Pulmonary edema - New-onset cerebral or visual disturbances 
*Proteinuria $>$5g is no longer considered for diagnosis nor is IUGR for 'severe'

3.4. Outcome variables: see attached data dictionary (Appendix I). I will plan to work with my prior IRB application request (IRB number 2016-006) using Peridata and Meriter for variables and have a prospective report built to extract patient data from for patients enrolled in this study.

4. Study procedures

4.1. Training and certification of staff and centers

Training of staff and pilot testing of procedures are crucial to standardized study procedures including BP measurement, quality control and data quality. We will provide central training for study staff. Additionally, any staff members consenting patients will undergo training specific to the current consenting procedures. Refresher courses will be provided through webinar technology on a yearly basis or as needed. All training related to the study will be logged in the study's regulatory binder.

Clinical site initiation to enroll and randomize participants is dependent upon completion of preliminary tasks. These tasks include completion of appropriate regulatory approvals

(IRB) and letters of agreement. Site training receipt of study equipment and development of a recruitment plan will be necessary.

4.2. Screening for eligibility and consent

For aims 1-5

Inpatient

We will screen for subjects on a daily basis by reviewing the patients admitted to postpartum unit. Patients will be approached if the electronic medical record indicates a diagnosis of hypertension or the patient meets the blood pressure criteria for enrollment. This screening will be performed by the mobile health nurse providing support for this program or the research coordinator as needed. If a patient is identified, the patient's nurse or care provider will be contacted to ask the patient if they are interested in learning more about the study.

Outpatient

I have also met with the providers providing obstetrical care to patients (midwives and physicians who practice at UW Health- [name], UW Health- Fitchburg, UW Health- West, UW Health- West Towne, UW Health- Union Corners, Associated Physicians) who express interest in providing this experimental clinical program for their patients. Providers may discuss this project with their patients who have hypertension affecting their pregnancy. They will also have access to the patient brochure and can give this to the patients they believe meet criteria for the study. If they identify a patient who is interested in participating they will directly contact a member of the research team to further discuss enrollment with the patient. In addition, the floor nurses will know the inclusion criteria and may contact a member of the research team for recruitment, however this is not expected.

Finally, a patient can inquire and express interest in participating the program and contact the research coordinator directly with the phone number contact provided in the study flier. The patient inclusion and exclusion criteria will be verified as well as the participant's interest in the study. The informed consent process will be conducted by trained research staff and will include all aspects of the study and full disclosure of the risks, benefits, and alternatives. The study consent and HIPPA authorization form (see appendix) will be signed after all questions have been discussed and answered.

4.3. Data management:

Data variables will be stored in REDCap. REDCap (Research Electronic Data Capture) is a browser-based, metadata-driven software solution and workflow methodology for designing clinical and translational research databases. It is a HIPAA compliant system exclusively used for investigator initiated studies and has wide use in the academic research community. You can learn more about REDCap at:

[https://en.wikipedia.org/wiki/Redcap_\(Research_Electronic_Data_Capture\)](https://en.wikipedia.org/wiki/Redcap_(Research_Electronic_Data_Capture))

Study management will be maintained using Oncore. OnCore is a centralized clinical research management software program that allows researchers to use one program to manage all components of clinical research while maintaining consistency, data integrity and compliance across the institution.

4.4. Recruitment and retention

- **Staff**

- 4.4.1. Staff training and education prior to initiation of the trial for active members of the study team.
- 4.4.2. General education regarding the trial to all staff providers (physicians, nurses, medical assistants to enhance support of the trial).
- 4.4.3. Staff education on a 6-month schedule for new staff and further training as needed.
- 4.4.4. Interval reports back to participating faculty/nurses to share stories of success or patient feedback to encourage continued participation.
- **Study subjects**
 - 4.4.1. We will place a study information sheet titled “The UnityPoint Health-Meriter Hypertensive Study” in the patient enrollment paperwork for all patients admitted to Labor and Delivery. This will sheet will allow research staff to collect data on all patients with respect to their hypertension diagnosis in the Peripartum period. We will be using this data primarily for the control group for aims 2-3.
 - 4.4.2. Once a patient is identified and agrees to participate we will give them a separate patient brochure to further detail the study. This will be directly given to the patients by their nurse once admitted to the postpartum unit.
 - 4.4.3. A member of the research team trained in consenting procedures will then meet with the subject to review the informed consent document. After the researcher reviews the document, the subject will be allowed to ask questions and given sufficient time to contemplate participation. If the patient chooses to participate, they will sign the informed consent document.
 - 4.4.4. Incentives: Subjects will be given a pack of diapers at enrollments and a \$15 gift card at completion of the study (6 weeks PP visit) to encourage completion of the trial endpoint.
 - 4.4.5. Care reminders will be sent via the Honeywell Genesis Device by the UnityPoint at Home telehealth nurse. The purpose of this is to remind and encourage daily vital reporting.
 - 4.4.6. Patient surveys for understanding how to improve the system

5. Pre-enrollment evaluation

- 5.1. Prior to enrollment, the mobile health nurse or research staff will confirm diagnoses utilizing the table above.
- 5.2. If the subject agrees to participate, the research coordinator will obtain informed consent.
- 5.3. To review eligibility, the patient will have a general physical exam, review of their vital signs, and pertinent laboratory assessments (hematocrit, platelet count, creatinine, urine protein volume, liver function tests) performed as standard of care and will be reviewed in the electronic medical record.
- 5.4. This baseline information will be obtained and entered into the study database and if the subject meets inclusion criteria the subject will be considered on study.
- 5.5. Enrollment is expected to occur over a 1-year time period.

6. Intervention and Follow-up

Patients will be identified for potential enrollment starting in the antepartum period (time of admission for delivery of baby) if they meet criteria for a hypertensive related disorder of pregnancy as deemed by the minimum criteria of SBP ≥ 140 or DBP ≥ 90 on two occasions

at least 4 hours apart. The planned consent can occur on admission prior to delivery or postpartum, however will not occur if the patient has any evidence of labor. The preference will be consenting postpartum. The exception may be for patients with known chronic hypertension or a diagnosis of preeclampsia and they are admitted with this diagnosis. Patients may be given the program brochure to read and would have adequate time to express interest or hear more about the project if they desire. If the patients then meet criteria for treatment of hypertension postpartum as deemed by the threshold inclusion criteria for this study, SBP ≥ 140 or DBP ≥ 90 or standard of care (SBP ≥ 150 or DBP ≥ 100) on two occasions at least 4 hours apart then medication will be initiated prior to discharge from the hospital.

Devices and instructions will be provided by UnityPoint at Home. They will be given instructions on proper techniques for blood pressure by the labor & delivery nurses, the mobile health nurse or research coordinator if needed. It will be expected if the teaching cannot be performed by one of the nurses they will contact the research coordinator to provide this training. All individuals will have had training for proper blood pressure measurement technique prior to providing this training. The patients will be required to take the blood pressures in a seated position with their arm at heart level. Three values should be obtained and an average of these values will be used in our assessment of daily blood pressure. The patient will also be given instructions on warning signs of preeclampsia or severe hypertension and blood pressure thresholds to call the mobile health nurse or their primary obstetric clinical provider or nurse.

Once discharged from the hospital the patient will initiate their home blood pressure/weight measurements. They will be asked to take a total of three blood pressures everyday (spread out no more than five minutes apart) to validate there are not erroneous values submitted. The blood pressures and weight values will be submitted via the Honeywell device and these values will be delivered to the mobile health nurse platform. These values will need to be manually uploaded into the study database program in REDCap. The values and patient concerns will be reviewed daily by the mobile health nurse with a flowsheet algorithm that directs them when to continue with current care plan or the need to contact the physician for the patient. The patient will be contacted by a mobile health nurse on days 2 and 7 post discharge. Additionally the patient may be contacted by the mobile health nurse based on the flowsheet algorithms and patient concerns (if applicable). A telehealth note will be put into EPIC when contact with the patient is had by phone or video teleconferencing. This note will be cc'd to the primary provider for review. Daily vital signs will eventually be an automated process into EPIC, however until this is possible it will be a manual entry performed daily by the mobile nurse.

Follow Up Procedures for Patients

Patients will receive continued care surveillance whether they are on or off medication if their blood pressures remain (SBP ≤ 150 or DBP ≤ 100) and they are not having any concerning symptoms. If they are on treatment with antihypertensive medication at discharge from the hospital the goal is for patients to remain with normal to mild range blood pressures and they will require the medication be titrated upwards to achieve adequate control (SBP ≤ 140 -150 or DBP ≤ 90 -100) as needed. If severe hypertension develops after discharge, and the blood pressures are SBP ≥ 150 or DBP ≥ 100 and the patient is not on medication we will recommend initiating medication as an outpatient. Alternatively, the medication may need to be titrated downward or discontinued if indicated due to the patient development of hypotension (SBP ≤ 90 or DBP ≤ 60).

The mobile health nurse will be reviewing the incoming blood pressures daily. Options for the enrolled patients care management are to report the concerning vital signs to the

patients primary provider or the primary provider can agree to have the Perinatal Service providers manage the abnormal vital signs. All providers for the enrolled patients are contacted and informed of enrollment and then typically they plan for the patients to be followed and managed with the mobile health team and any concerning vitals are addressed by the Perinatal Service and then communicated regarding any management decisions by EPIC-electronic medical charting.

Concerning vital signs are SBP ≥ 150 or DBP ≥ 100 or SBP ≤ 90 or DBP ≤ 60 , which is the same as prior to discharge from the hospital. After the program began using the above paragraph which outlines need for medication initiation or management – it was acknowledged patients were requiring the initiation and management of their vital signs or medications often, i.e. approximately 40-50% of the patients. Therefore, the mobile health nurses needed a written document with the standard practice to determine the thresholds patients would need to initiate or titrate medications up or down. Therefore we developed algorithms as proposed in this modification that would help manage this care. In addition, as needed the patient will be instructed to call their provider as needed for any concerning vital signs or symptoms if the nurses are not available or as needed. If the patient does not have any concerning symptoms the abnormal vital signs will be discussed with the patient by the patient's provider or the nurse. If the patient is asymptomatic then there is the ability to refer to the management algorithm and then initiate medication or increase/decrease the dose of the medication per the algorithm. The algorithm is based off the standard of care – it is just to ease the communication and care coordination of the patients. The mobile health nurse will notify a doctor with initiation of medication.

It is expected that the patients with gestational hypertension or preeclampsia diagnoses will be able to titrate off of the antihypertensive medication between 14 -42 days postpartum. The recommendation to discontinue the antihypertensive medication can be performed if the patient has (SBP ≤ 120 or DBP ≤ 80) by the 14-day follow-up visit. If they are unable to do so by the 42-day follow-up visit they will likely be diagnosed with chronic hypertension (persistent elevation of blood pressure SBP ≥ 140 or DBP ≥ 90 by 12 weeks postpartum. It is expected that patients with chronic hypertension may need to continue this therapy beyond the study endpoint of 42 days.

Due to current ACOG recommendations, the patients will be recommended to remain in the hospital for 3 days postpartum when they have a diagnosis of hypertensive related disorders in pregnancy. If the patient is discharged prior to 3 days they will have an outpatient office visit for a blood pressure evaluation at day 3. If they are discharged on day 3 they will then have planned outpatient clinic blood pressure evaluations on days 5-7 and at 14 days postpartum. As long as the patient is normotensive and clinically stable then the patient will have the last scheduled follow-up exam at approximately 6 weeks (42days) postpartum.

A planned **patient satisfaction survey** will be administered at 6 weeks (42) post-discharge using email or in person at their clinic visit. This may be sent electronically through the mobile app system if possible to allow for best patient access if they are following up at numerous different clinics, vs at the actual clinic visit. We will assure all participating clinics have the survey and a sealed box to protect the patient's identity.

The patients will be instructed to call their primary provider once discharged from the hospital if they do not achieve adequate continued blood pressure control after discharge or they have concerns of developing severe symptoms concerning for worsening disease-listed below-if not addressed through the surveillance as discussed above through the mobile health surveillance and management algorithm. Hospital readmission will be

dependent on provider discretion, however indications would depend on evaluation of patients' clinical symptoms of severe hypertension with SBP ≥ 160 or DBP ≥ 110 , with the addition of end-organ effects (cerebral or vision disturbances, neurologic symptoms, pulmonary edema, or lab abnormalities as defined in table 4.3) that cannot be explained by medication non-compliance or inability to increase the dose of the medication to achieve adequate control.

If the situation dictates another antihypertensive due to other medical comorbidities (such as asthma) then another antihypertensive medication can be considered. Our recommendation would be to consider use of a calcium channel blocker (specifically Nifedipine).

Provider Survey:

The Office Supervisor for the Perinatal Administration at UPH - Meriter hospital will generate a list of providers with delivery privileges for the research team. Each provider will be invited by email to complete the survey. We are requesting a Waiver of Consent and an Exemption from HIPAA as a completed survey implies consent, and there is no private health information involved in this part of the research.

A Provider survey (uploaded in iRIS) will be linked within an email (script attached as separate study document). This email will be sent by UPH-Meriter staff, to their identified list of providers (those who have delivery privileges at UPH-Meriter). They will complete the survey in Qualtrics in which no identifying information will be collected. The email will be sent a total of 3 times.

UPH-Meriter Telehealth Clinical Program:

We will retrospectively review the patient data in Peridata for these 358 patients. We will collect home vital sign data to assess blood pressure trends from early pregnancy through pregnancy and postpartum. No new data fields will be added to the data collection.

Subject withdrawal policy

Withdrawals are considered subjects that have been enrolled but are deliberately omitted from the analysis. This study will be analyzed on the intention-to-treat principle, so that all subjects who were enrolled will be included in the analysis. To minimize the amount of missing data, subjects will only be randomized after they have undergone appropriate diagnostic tests, eligibility has been confirmed by the research coordinators. If a subject is randomized but later decides to discontinue study participation, they are asked in the consent form to allow follow-up via medical record review. For further information on subjects who discontinue participation, see Section 9.2. Every effort will be made to follow all patient outcomes via medical records.

7. Statistical considerations

